As for the preliminary examination for recruitment, patients reporting for baseline examination will be required, after brushing their teeth with the supplied toothpaste and toothbrush on the morning of the visit, to have refrained from 1) any other oral hygiene procedures or use of chewing gum, and 2) eating or drinking, except for drinking water, prior to the visit. The baseline examination will assess tactile and cold air sensitivity. (The procedures for each of these tests are described below). For each patient eligible to participate in the study, one or more hypersensitive teeth that satisfy the tactile and cold air hypersensitivity enrolment criteria will be identified for evaluation throughout the study. For each assessment visit, including the baseline examination, sensitivity must be triggered by application of a tactile stimulus and a cold air blast stimulus, and the level of sensitivity recorded.

For each patient completing the washout period, the result obtained according to the selection criteria at the preliminary examination for recruitment shall be compared with the result obtained at baseline examination. Only patients who 1) show a worsening of DHS or 2) maintain the same level of DHS over the duration of the washout period shall be selected and enrolled as subjects to participate in the trial, i.e. only patients who at the baseline examination meet the qualifying criteria, namely a Yeaple value of 30g or less and a VAS score in response to cold air stimulus of 30mm or more, will be accepted as subjects. As shown in the section explaining tactile stimulus, however, though the Yeaple criterion for acceptance in the study will be sensitivity at a pressure of 30g or less, in carrying out the baseline examination, the Clinical Examiner will apply pressure starting from a load of 10g, and increasing by increments of 10g, up to a maximum of 80g.

Test Products

The test products shall contain respectively 0% nano-HAP (placebo), 15% nano-HAP, and 5% KNO₃ (positive control).

Randomization/Allotment to Test Product Groups

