A total of 192 subjects diagnosed with DHS and who have met all necessary requirements for selection as subjects in the trial will be stratified into three balanced groups according to age, gender and VAS score in response to cold air stimulus at the time of baseline examination for final selection of subjects eligible to participate in the trial (64 per group). One of the three test products shall be randomly assigned to each of the three groups. The 0% and 15% nano-HAP-containing toothpastes and the 5% KNO₃ toothpaste shall be randomly coded as either A, B, or C by the manufacturer or Sponsor, and the code shall not be disclosed until all statistical analysis is complete.

Clinical Procedures

Immediately following the baseline sensitivity examination, each patient who qualifies to become a subject in the trial will be given and make the first use of his/her allotted test toothpaste, under the supervision of the Study Coordinator, after the latter has confirmed and recorded the weight of the tube. During the next 8 weeks, subjects will be required to brush their teeth twice daily with their allotted test product, as instructed, and not to take any food or drink for at least 30 minutes after brushing except for drinking water. A diary covering the duration of the study will be provided to each subject to (1) keep a record of number of times of brushing each day, and (2) record the name of any medication taken during the study period. All subjects will be asked to maintain their normal dietary habits. However, the use of oral hygiene products that are not related to this clinical trial, such as mouthwash and prescription medicine, along with dental clinic visits, dental treatment, professional plaque removal, whitening, use of pain relievers or commercial hypoallergenic products as well as use of narcotics, anti-inflammatory drugs, conventional analgesics, anticonvulsants, antihistamines, antidepressants, sedatives and other psychotropic drugs shall be prohibited throughout the course of the study.

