Information concerning any adverse events will be obtained by the Clinical Examiner from the subjects at the time of sensitivity assessment. All observed or voluntarily reported adverse events regardless of test group or suspected causal relationship with a test product shall require immediate notification within 24 hours to the IRB and the Sponsor or its designated representative, during a reporting period beginning from the time that the subject first provides informed consent, which is obtained prior to the start of the clinical study, i.e. prior to the subject undergoing any study-related procedure and/or receiving any test product, through to and including 30 calendar days after the last administration of the test product. Any adverse event occurring any time after the reporting period must be promptly reported to assess whether it meets the criteria for classification as a serious adverse event requiring immediate notification to the Sponsor or its designated representative. The Principal Investigator is required to assess causality, and for all adverse events, sufficient information should be obtained by the Principal Investigator to try to determine the causality of the adverse event. For adverse events with a suspected causal relationship to a test product, follow-up by the Principal Investigator is required until the event or its sequelae are resolved or stabilized at a level acceptable to the Principal Investigator, and the Sponsor concurs with that assessment.

STATISTICAL PROCEDURES:

Product Efficacy Data Analysis:

Efficacy outcomes: The primary efficacy outcome will be the decrease in cold air stimulus sensitivity (VAS score) from baseline to 8 weeks. The secondary efficacy outcome will be the increase in tactile stimulus force from baseline to 8 weeks. Additional outcomes will include changes in cold air stimulus sensitivity and tactile stimulus force from baseline to 4 weeks.

(1) Data Analysis for Efficacy of the Primary Evaluation Item

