Comparisons among the three groups for differences in the primary and secondary efficacy outcomes at each time point will be analyzed using analysis of covariance; because of the stratified randomization, age, gender, and baseline VAS cold air sensitivity will be included as covariates. Pre-planned post-hoc comparisons include: 1) pair-wise comparisons of the test product and the positive control against the placebo, to demonstrate effectiveness and 2) 95% confidence intervals (CI) for the ratio of means for the nano-HAP test product to the positive control to demonstrate non-inferiority of the test product with the positive control. Non-inferiority will be demonstrated if the lower

bound of the 95% CI falls within the 20% non-inferiority margin. If the data are log-normally distributed, then the analyses will be done on the log-transformed data. If the 95% CI for the difference between the test paste and the positive control is transformed back to the original scale, the back-transformed CI is a 95% CI for the ratio of means. If data are normally distributed, the 95% CI will be computed using Fieller's theorem, and the other condition that must be met to show non-inferiority is that the reference (i.e. positive control) mean must be significantly different from zero using a one-sided test. A 5% significance level will be used for all tests. From the results obtained for the placebo and positive control groups, it will be confirmed whether the non-inferiority margin used in the trial (20%) was appropriate or not.

(2) Data Analysis for the Efficacy of the Secondary Evaluation Item

Repeated measures analysis of covariance will be used for comparison between the 4-week and 8-week outcomes within each group. Interactions of the treatment effect with age, gender, and tactile sensitivity will be examined to evaluate significance of differential effects of the treatment by patient characteristics.

Sample Size Calculation

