Alpha is the probability of rejecting a true null hypothesis.

Summary Statements

Group sample sizes of 38 in the first group and 38 in the second group achieve 80% power to detect non-inferiority using a one-sided, two-sample t-test. The margin of non-inferiority is 20%. The true ratio of the means at which the power is evaluated is 1.000. The significance level (alpha) of the test is 0.050. The COV of both groups are assumed to be 0.400.

With a sample size of at least 57 subjects per group completing the study, a non-inferiority test of means using two one-sided tests achieves 80% power at a 5% significance level for cold air stimulus sensitivity when the true ratio of the means is 1.000 and the non-inferiority limit of the mean ratio is 20%. Because the COV for tactile stimulus force is smaller, the study will have higher power for that outcome. To allow for 10% dropout, the study will enroll 64 subjects per group (192 subjects in total). Sample size calculations were performed using PASS 2019 (Kaysville, UT).

Dropout-Inflated Sample Size

Dropout Rate	Sample Size			Dropout-Inflated Enrollment sample size			Expected Number of Dropouts		
	N1	N2	N	N1'	N2'	N'	D1	D2	D
10%	38	38	76	43	43	86	5	5	10
10%	57	57	114	64	64	128	7	7	14

Definitions

Dropout Rate (DR) is the percentage of subjects who are expected to be lost at random during the course of the study and for whom no response data will be collected (i.e. who will be treated as "missing").

[figure not shown]
N1, N2, and N are the evaluable sample sizes at which power is computed. If N1 and N2 subjects are evaluated out of the N1' and N2' subjects that are enrolled in the study, the design will achieve the stated power.

N1', N2', and N' are the number of subjects that should be enrolled in the study in order to end up with N1, N2, and N evaluable subjects, based on the assumed dropout rate.

After solving for N1 and N2, N1' and N2' are calculated by inflating N1 and N2 using the formulas $N1' = N1 / (1 - DR)$ and $N2' = N2 / (1 - DR)$, with N1' and N2' always rounded up. (See references A7, pages 52-53, or A8, pages 32-33.)

D1, D2, and D are the expected number of dropouts. $D1 = N1' - N1$, $D2 = N2' - N2$, and $D = D1 + D2$.

Chart Section

Criteria for Test Aborting and Drop-out

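### The tactile-force ANCOVA leaves out baseline tactile force; adding it uses data already collected and may gain a little precision

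*Combined protocol and SAP*

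**What the plan says.** In the combined protocol and SAP, Statistical Procedures section (1) gives one ANCOVA for between-group comparisons of both the primary and secondary outcomes at every time point. On covariates it says: "because of the stratified randomization, age, gender, and baseline VAS cold air sensitivity will be included as covariates".

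The tactile outcome is a change score. Under Efficacy outcomes: "The secondary efficacy outcome will be the increase in tactile stimulus force from baseline to 8 weeks". The change to 4 weeks is an additional outcome.

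Under Randomization/Allotment to Test Product Groups, subjects are "stratified into three balanced groups according to age, gender and VAS score in response to cold air stimulus". Tactile force is not an allocation factor.

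Tactile force is nevertheless measured at the baseline examination. Final Selection: Baseline Sensitivity Measurement states that "the Clinical Examiner will apply pressure starting from a load of 10g, and increasing by increments of 10g", to a maximum of 80 g, and accepts only subjects who respond at 30 g or less. The same section allows more than one tooth per subject: "one or more hypersensitive teeth that satisfy the tactile and cold air hypersensitivity enrolment criteria will be identified".

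The only place where tactile sensitivity appears as a model term is section (2): "Interactions of the treatment effect with age, gender, and tactile sensitivity will be examined".

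**The concern.** Each VAS comparison is adjusted for its own baseline. The tactile comparison is adjusted for the baseline of a different measurement and not for its own. The reason given, the stratified randomisation, explains why the three covariates are in the model. It is not a reason to leave baseline force out.

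A change score does use baseline, but it fixes the slope of follow-up on baseline at 1. Nothing in the documents supports exactly 1. Eligibility confines baseline to 10, 20 or 30 g for a single tooth, while follow-up can run to 80 g. If the true slope differs from 1, two things follow:

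- The residual variance of the tactile comparison is larger than it need be.
- In any one trial, (slope − 1) times the chance difference in baseline force stays in the estimated treatment effect.

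At stake is some precision on the secondary outcome and its 4-week counterpart. There is also a practical point: if a baseline imbalance in force is seen later, adjusting for it then would be a post-hoc choice.

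**Working it through.** **The plan's own figures.** Sample Size Calculation gives COV 0.5 (cold air) and 0.4 (tactile force at 8 weeks), margin 0.2, true ratio 1, one-sided alpha 0.05 and power 0.80. On the log scale, SD_log = √ln(1 + COV²) and ncp = −ln(0.8) / (SD_log·√(2/n)), with a noncentral t on 2n − 2 df.

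- COV 0.5, n = 57: SD_log 0.472, ncp 2.52, power 0.80557. Agrees.
- COV 0.4, n = 38: SD_log 0.385, ncp 2.52, power 0.80419. Agrees.
- COV 0.4 at the planned n = 57: ncp 3.09, power 92.3%. This fits the statement "Because the COV for tactile stimulus force is smaller, the study will have higher power for that outcome".

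None of these figures uses covariate adjustment, so the required number does not depend on this point.

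**Inputs for the gain.** From the plan: 57 completers per group, and baseline force limited to 30 g or less in 10 g steps. Assumed, because the documents give none of them: baseline SD SDb = 7 g, 8-week SD SD8 = 15 to 25 g, correlation r = 0 to 0.6.

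**Formulas.**

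- Variance ratio, with against without baseline force: SD8²(1 − r²) / (SD8² + SDb² − 2·r·SD8·SDb).
- Slope = r·SD8/SDb.
- SE of the baseline difference between two groups = SDb·√(2/57). For 7 g this is 1.31 g, so a 2-SE imbalance is 2.62 g.
- Carry-over into the change-score estimate = (slope − 1) × imbalance.

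**Results, SDb = 7 g.**

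| SD8, r | Variance ratio | Slope | Carry-over of a 2-SE imbalance | SE of change difference | Carry-over in SEs |
|---|---|---|---|---|---|
| 20 g, 0.3 (middle) | 364/365 = 0.997 | 0.857 | −0.37 g | 3.58 g | 0.10 |
| 15 g, 0 | 225/274 = 0.821 | 0 | −2.62 g | 3.10 g | 0.85 |
| 25 g, 0.6 | 400/464 = 0.862 | 2.14 | +3.00 g | 4.03 g | 0.74 |

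Over the whole range the ratio runs from 0.821 to 1.000. The median gain is about 2.6% on a fine grid and higher on coarse ones, so the range is the figure to rely on.

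**Sensitivity to the baseline SD.**

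- SDb = 5 g, as might arise if several teeth are averaged: the 2-SE imbalance is 1.87 g and the ratio runs from 0.80 (400/500, at 25 g and r = 0.6) to 1.00. The middle point is again 0.997. Carry-over is 0.37 g at the middle and runs from −1.87 to +3.75 g.
- SDb = 10 g, the most that baseline values of 10 to 30 g allow: the ratio at 15 g and r = 0 is 225/325 = 0.69, a cut of 31%. With an 8-week SD of 12 g it is 144/244 = 0.59, a cut of 41%.

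**Simulation.** Three groups of 57 were simulated under the planned ANCOVA, with and without baseline force. Assumptions were a residual SD of 17 g, baseline uniform on 10, 20 and 30 g, and the other covariates unrelated to force. The mean SE of the nano-HAP minus KNO₃ difference was:

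- slope 0: 3.56 g without, 3.22 g with;
- slope 0.5: 3.30 g without, 3.22 g with;
- slope 1: 3.21 g without, 3.22 g with.

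So adjustment helps when the slope is away from 1 and costs almost nothing when it is 1.

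**Against the planned number.** An 18% loss leaves 57 × 0.82 ≈ 47 effective subjects per group, against the 38 needed for tactile force. This is indicative only, because the COV of 0.4 describes force at 8 weeks, not its change.

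**The case against.** The strongest reply is that this is a preference. Adjusting for the allocation factors is a coherent, prespecified rule, the change score already uses baseline, and both models are valid under randomisation. Only a secondary outcome is affected, and it has spare power. All of that stands, and it is why the point is a minor improvement and not a fault.

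The interaction analysis in section (2) may also bring tactile sensitivity in as a main effect. It does not settle the matter. The text does not say that this model supplies the between-group estimate, or that tactile sensitivity there means the baseline value.

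Three cautions on the numbers also stand:

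- The SDs and correlation are assumed, and 18 to 20% is not a ceiling. A baseline SD near 10 g gives more.
- Carry-over is the variance loss seen conditionally on an imbalance, not a second harm added to it. The largest values combine a 2-SE imbalance with slopes of 2 to 3 that nothing in the documents supports.
- The formula compares an unadjusted change score with adjustment for baseline force alone. If baseline VAS, age or gender are related to baseline force, the gain over the planned model will differ. The simulation keeps those covariates in the model but treats them as unrelated to force.

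**Conclusion.** The concern holds as an optional improvement. Baseline tactile force is collected before allocation, is not balanced by it, and is not named as a covariate in the between-group tactile models. There is no bias on average, and no effect on the primary VAS analysis or the sample size.

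The omission itself is certain from the text. The size of the benefit is not: it rests wholly on the assumed SDs and correlation, and the middle of the assumed range shows almost no gain. The case for the change is that it costs next to nothing even when it brings no benefit.

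**What to change.** In section (1) of Statistical Procedures, state that the 4- and 8-week tactile-force models include baseline tactile force as a covariate alongside age, gender and baseline VAS. Define it as the subject-level value, computed in the same way as the follow-up value, since a subject may contribute more than one tooth. Leave the VAS models unchanged.

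The cost is one phrase in the SAP and one degree of freedom among about 171 completers (3 × 57). No new data, visits or subjects are needed. The change should be made before unblinding.

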Only patients who meet all initial screening criteria and provide written informed consent will be invited to proceed to recruitment screening for participation in the trial. Recruitment screening will consist of three steps, as described below: (1) a preliminary examination; (2) a 4-week washout period (for patients who meet the entry criteria during the preliminary examination); then (3) at the end of the washout period, evaluation and recording of each patient's baseline sensitivity level, as the basis for final subject selection.

(1) Preliminary Examination for Recruitment

Patients eligible for recruitment screening will report to the clinical research facility having refrained from 1) oral hygiene procedures or use of chewing gum for 8 hours, and 2) eating or drinking for 4 hours, except for drinking water, prior to the visit. The examination will include checking the patient's medical history and medication use, and a thorough oral examination by the Clinical Examiner, with evaluation of sensitive teeth. Tooth sensitivity will be assessed by a positive response to tactile and cold air stimuli, and the entry criteria for parameters assessed at this preliminary examination for recruitment will be 1) a positive response to tactile stimulus using a Yeaple probe at 30g force (standardized application for every subject), and 2) a VAS score of 30mm or more assessed using a one-second cold air blast from a standard dental unit air syringe. (The procedures for each of these tests are described below).

(2) Washout Period

Only patients who meet the entry criteria in the preliminary examination will proceed to the washout period. They will be assigned to use a toothpaste not containing either fluoride, hydroxyapatite or KNO_3 , with an adult soft-bristled toothbrush, for a period of four weeks. The toothpaste and toothbrush will be used in place of the patient's normally used toothpaste and toothbrush, and will be supplied by the Sponsor. The patient will be instructed, after wetting the brush, to apply one inch (2.5cm) of the supplied toothpaste per brushing and to brush for 3 minutes by the scrubbing method twice daily, in the morning and last thing before bed at night, rinsing out the toothpaste with 10ml of water for 10 seconds after brushing. Patients will be asked to return to the clinical research facility for assessment at 4 weeks.

(3) Final Selection : Baseline Sensitivity Measurement

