VAS will be used within 2 minutes of stimulus application to evaluate the intensity of sensitivity on each measurement occasion: preliminary examination for recruitment, baseline examination, and examination after 4 and 8 weeks. The VAS scale, which must be explained to the subject, consists of an unmarked horizontal straight line, 100mm long, drawn on a sheet of paper, with the beginning and end representing no pain and maximum pain respectively. Following stimulus application as described above, the Clinical Examiner shall ask the subject to draw a vertical mark on the line, indicating how much pain he/she just felt, with "no pain" being on the far left of the scale at 0mm and "pain as bad as it can be," i.e. the maximum pain the subject could experience, being on the far right at 100mm. The distance between 0mm and the mark made by the subject shall then be measured in mm by the Clinical Examiner and recorded as the subject's VAS score, i.e. his/her indicated level of pain.

Calibration of the Clinical Examiner

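### The cold-air ANCOVA leaves out the preliminary-examination VAS, a second pre-randomisation score; adding it is a cheap efficiency gain, probably modest and possibly nil

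*Combined protocol and SAP*

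**What the plan says.** The primary outcome is "the decrease in cold air stimulus sensitivity (VAS score) from baseline to 8 weeks" (Efficacy outcomes). Under Statistical Procedures (1), groups are compared by analysis of covariance. Because the randomisation is stratified, "age, gender, and baseline VAS cold air sensitivity will be included as covariates".

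The VAS section has the scale completed "on each measurement occasion: preliminary examination for recruitment, baseline examination, and examination after 4 and 8 weeks", so there are two cold-air scores before treatment and two after.

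- **Preliminary score.** Entry to washout requires "a VAS score of 30mm or more assessed using a one-second cold air blast" (Preliminary Examination for Recruitment). Patients attend having refrained from "oral hygiene procedures or use of chewing gum for 8 hours".
- **Baseline score.** After washout, "the result obtained according to the selection criteria at the preliminary examination for recruitment shall be compared with the result obtained at baseline examination" (Final Selection: Baseline Sensitivity Measurement). Enrolment is limited to patients who "show a worsening of DHS or 2) maintain the same level of DHS over the duration of the washout period". The same sentence then restates this as meeting the tactile and 30 mm VAS thresholds at baseline. Patients attend having brushed that morning with the washout paste.

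Every randomised subject should therefore have both scores. No analysis in the plan uses the first.

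**The concern.** A single VAS mark after a one-second air blast is a noisy reading of a subject's sensitivity. The plan recognises this. Its stimulus section lists factors that can alter perception and allows repeat or sham applications, and its calibration section schedules duplicate examinations. When one reading is noisy, a second pre-treatment reading of the same quantity usually carries prognostic information that the first misses.

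The preliminary score is fixed before allocation, so adding it as a pre-specified covariate introduces no bias and leaves the estimand alone. The plan gives no reason for omitting it. What is at stake is precision only: the width of the interval for nano-HAP against KNO₃ and of the comparisons with placebo on the cold-air outcomes.

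**Working it through.** **1. The plan's own figure.** Inputs from Sample Size Calculation: COV 0.5, ratio bound 0.80, true ratio 1.0, one-sided alpha 0.05, 57 evaluable per group. On the log scale, σ = √ln(1 + 0.5²) = 0.472 and the margin is −ln 0.8 = 0.223. The noncentrality is 0.223 / (0.472 × √(2/57)) = 2.52 on 112 df. Power is 0.8056, matching the stated 0.80557. Dropout: 57/0.9, rounded up, is 64, as stated. No covariate adjustment enters this calculation.

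**2. Formula for the gain.** Let a = corr(preliminary, baseline), b = corr(baseline, week 8) and c = corr(preliminary, week 8). With baseline alone the residual fraction is 1 − b². Adding the preliminary score removes a further (c − ab)²/(1 − a²). If c = ab, so that the preliminary score predicts week 8 only through baseline, the gain is exactly zero.

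**3. Assumed inputs.** The documents give COVs only. Assume reliability r = 0.5 to 0.8 for one VAS reading, and that underlying sensitivity explains q = 30 to 50% of week-8 variance. Then a = r and b² = c² = rq, and the proportional reduction is rq(1 − r)²/(1 − r²) divided by (1 − rq). Before any selection:

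| r | q | Baseline only, 1 − rq | Removed by preliminary | Reduction |
|---|---|---|---|---|
| 0.5 | 0.3 | 0.85 | 0.15 × 0.25/0.75 = 0.050 | 5.9% |
| 0.5 | 0.5 | 0.75 | 0.25 × 0.25/0.75 = 0.083 | 11.1% |
| 0.8 | 0.3 | 0.76 | 0.24 × 0.04/0.36 = 0.027 | 3.5% |
| 0.8 | 0.5 | 0.60 | 0.40 × 0.04/0.36 = 0.044 | 7.4% |

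**4. Selection at entry.** Enrolment conditions on both scores, which shrinks the separate information in the first. By simulation:

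| Assumption | Both scores ≥ 30 mm | Also baseline ≥ preliminary |
|---|---|---|
| r 0.5–0.8, q 30–50% | about 3–9% | about 1–4% |
| Same, with VAS mean 50 and SD 20 | about 3–8% | about 1–3% |
| Equal correlation 0.3–0.7 between all occasions | about 3–16% | about 1–7% |

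The enrolment sentence can be read either way, so both columns are live.

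**5. Cost.** The planned model has 3 arm terms and 3 covariates. With 3 × 57 = 171 subjects, residual df go from 165 to 164. Expected variance inflation is 164/163 = 1.006, about 0.6%.

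**6. Net effect on power.** Multiply each variance ratio by 1.006 and use the formula in step 1 at 57 per group. The reference is one-sided 0.025, which is what a two-sided 95% CI implies. Unadjusted power there is 70.5%.

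| Gross reduction | Net variance ratio | Change in power |
|---|---|---|
| 0% | 1.006 | −0.3 points |
| 1% | 0.996 | +0.2 |
| 3% | 0.976 | +1 |
| 4% | 0.966 | +1.5 |
| 9% | 0.916 | +3.8 |

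In subjects, before cost, 1 to 9% is worth 57/0.99 − 57 = 0.6 to 57/0.91 − 57 = 5.6 per group.

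**The case against.** The strongest objection is that nothing here is wrong. The covariates are the stratification factors, they include the latest pre-treatment value of the primary measure, and the stated power relies on no adjustment at all. That stands, so the point is an improvement and not a correction.

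The two scores are also not clean replicates. The first is taken on the patient's usual toothpaste after 8 hours without oral hygiene; the second follows four weeks of washout paste and brushing that morning. Study teeth are identified at the baseline examination, so the first score may relate to other teeth. This does not affect validity, but it can lower the gain, and it means the covariate needs a definition.

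The simulation builds in some benefit, because it treats both scores as one true sensitivity plus independent noise. It also models the week-8 value. With baseline VAS in the model, that gives the same residuals as the raw decrease, but the gain has not been shown for log-transformed decreases.

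A reader might infer that precision is gained at no cost. The documents do not support this: the cost is small but not zero, and the benefit rests on correlations they do not report. A reader might also infer that the change repairs the 70.5% power. It does not. That figure ignores the baseline adjustment already planned. On the assumptions used here, baseline VAS explains rq = 15 to 40% of week-8 variance before selection, which puts power at one-sided 0.025 at about 77 to 90%. The shortfall arises from sizing at one-sided 0.05 while judging by a 95% CI, which is a separate matter.

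**Conclusion.** The point holds as a missed efficiency. A pre-randomisation cold-air VAS that should exist for every enrolled subject is left out of the model, and including it would be valid. Under the stated reliability and prognostic assumptions, the gain is about 3 to 9% of residual variance if only the 30 mm thresholds select subjects. It is about 1 to 4% if baseline must also be no lower than preliminary. Net of cost, this is roughly 0 to 4 points of power. If the preliminary score adds nothing beyond baseline, there is a loss of about 0.3 points. The direction is likely to be favourable; the size cannot be settled from the documents. The planned analysis is neither biased nor invalid without the change.

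**What to change.** In Statistical Procedures (1), add the preliminary-examination cold-air VAS as a covariate alongside age, gender and baseline VAS in the ANCOVA for the 8-week and 4-week cold-air outcomes.

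- **Define the value.** Use the score for the study tooth or teeth where one was recorded, otherwise the subject-level value. Combine across teeth in the same way as at baseline.
- **Fix it in time.** Make the change before unblinding. Because the product code is withheld until analysis is complete, it should also precede any look at outcomes by coded group.
- **Keep the planned model** as a sensitivity analysis, and leave the estimand and the 20% rule unchanged.

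The cost is one degree of freedom and a short rule on which preliminary score to use. No new visit, measurement or subject is needed. The mismatch between the one-sided 0.05 sample size and the 95% CI rule needs its own resolution.
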